Study Protocol and Statistical Analysis Plan

Title: Improvements in upper extremity function following intensive training are independent of corticospinal tract organization in children with unilateral spastic cerebral palsy: A clinical randomized trial.

NCT: 02918890

Date: 5/1/2014

Study Objectives

This study aims to test the hypothesis that improvements in upper extremity function following either constraint induced movement therapy (CIMT) or bimanual training depend on corticospinal tract (CST) laterality and type of training (unimanual vs. bimanual) in children with unilateral spastic cerebral palsy (USCP). Specifically, we predict that children with a maintained contralateral CST will respond equally to CIMT and bimanual training, while children with ipsilateral CST laterality will be less responsive to CIMT than bimanual training.

Study Design

All study procedures will be approved by the Institutional Review Boards of Teachers College, Columbia University, where the treatments will be conducted, the Burke Medical Research Institute, where TMS evaluations will be performed, and Weill Cornell Medicine, where magnetic resonance imaging (MRI) will be performed.

We will recruit participants from clinics in the NYC area, our website (<http://www.tc.edu/centers/cit/>), ClinicalTrials.gov (NCT02918890), and online support groups. We will obtain written informed consent and assent from children and their caregivers.

We will randomize participants to receive either 90 hours of CIMT or Hand-Arm Bimanual Intensive Training (HABIT) after they complete all baseline outcome measures. Block randomization will be implemented for each cohort of participants, with each cohort stratified by age, sex, baseline hand function and CST connectivity pattern as closely as possible. Randomization will occur offsite using concealed allocation to receive either CIMT or HABIT. Intervention will be delivered in a day-camp model for 6 hours/day over 15 days for a total of 90 hours.

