The inclusion criteria will be: 1) ages 6 to 17 years, 2) diagnosed with USCP 3) capable of participating in a 15 day, 6 hours/day day camp while separated from caregiver(s), 4) capable of following directions regarding hand use and testing, 5) capable of communicating needs, 6) mainstreamed in age-appropriate school classroom, and 7) able to lift the more affected arm 15cm above a table surface and grasp light objects. The exclusion criteria will be: 1) unwillingness to comply with instructions or other behavioral issues making delivery of an intensive therapy infeasible, 2) health problems unassociated with hemiplegia, 3) visual impairment that could interfere with participation, 4) orthopedic surgery on the more affected hand within 1 year, 5) presence of metallic objects in the body, and 6) botulinum toxin in the more affected upper extremity within the past 6 months or intended treatment within the study period, 7) seizures after the age of 2 years, 8) family history of seizure disorders, 9) current medication use to lower the seizure threshold, 10) claustrophobia, or 11) pregnancy.

We aim to recruit 82 participants based on sample size calculations from results of the Assisting Hand Assessment (AHA) and Jebsen-Taylor Test of Hand Function (JTTHF) outcomes of a prior CIMT/HABIT randomized controlled trial and pilot data.

Methodology

Children will participate in an intensive hand training intervention using either one (CIMT) or both (HABIT) hands. During the intervention, children will be paired with a trained interventionist, with an interventionist:child ratio of at least 1:1. We will recruit and train physical and occupational therapists, graduate students in kinesiology/neuroscience, speech pathology, and psychology, and undergraduates to be interventionists. Interventionists will be supervised by experienced PT/Ots. Both the interventionists and supervisors will be blinded to CST connectivity patterns. Prior to the intervention, a training session will be conducted by the supervisors for standardization based on the established manual of procedures for CIMT and HABIT. Fidelity will be reinforced by supervisors during the day camp and daily post-camp meetings. Participants receiving CIMT and HABIT will be located in separate rooms, with each room being supervised by experienced PTs/OTs who will model and ensure uniformity of treatment. Each day, interventionists will attend team meetings to discuss the progress and needs of each child.

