participant will be screened for movement artifact, and slices showing artifact will be removed. Since images are obtained using 65 gradients, up to 30% of slices may be removed without compromising feasibility of tract reconstruction. Using DTI Studio, we will place region of interest seeds in the affected motor cortex and cerebral peduncle, and later in the unaffected motor cortex and cerebral peduncle. We will use tractography to find tracts that pass through both regions of interest. We will categorize each CST as present or absent. If there is a present CST on the affected side, the child will be categorized as having a contralateral CST. If there is not a CST present on the affected side, and a CST present on the other side, the child will be categorized as having an ipsilateral CST.

Statistical Analysis Plan

This will be an intention-to-treat study. If a child misses their 6 month follow-up assessment, we will impute their missing data based on the average change data for other participants in their subgroup. Statistical analyses will be performed using SPSS (IBM). A treatment (CIMT, HABIT) x CST connectivity pattern (contralateral, ipsilateral, bilateral) x test session (pre-, post-, 6 month) ANOVA with repeated measures on test session will be performed on all measures and Newman-Keuls post hoc tests will be performed where appropriate. Regression analyses will be done to determine predictors of outcomes. For children with a bilateral CST, correlations will be done between the LI and changes in outcome measures. Statistical significance will be considered at the $p<0.05$ level.

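### The only named follow-up test compares score means, so the plan has no test that places a difference in improvement in ipsilateral children

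*Combined protocol and SAP*

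**What the plan says.** Study Objectives predicts equal response to the two treatments in children with a contralateral CST, while "children with ipsilateral CST laterality will be less responsive to CIMT than bimanual training". Both parts are statements about change, compared between arms within a CST group.

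The Statistical Analysis Plan specifies a treatment "x CST connectivity pattern (contralateral, ipsilateral, bilateral) x test session (pre-, post-, 6 month) ANOVA with repeated measures on test session", which "will be performed on all measures and Newman-Keuls post hoc tests will be performed where appropriate". Pre-test is one level of the session factor, so the analysed means are score levels. The plan does not say which means are compared, which error term is used, or whether a significant interaction is needed first.

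Two other analyses are named. One is general: "Regression analyses will be done to determine predictors of outcomes". The other uses change explicitly but only in one group: "For children with a bilateral CST, correlations will be done between the LI and changes in outcome measures". On significance the plan says: "Statistical significance will be considered at the $p<0.05$ level".

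Under Study Design, allocation is by blocks within cohorts, "with each cohort stratified by age, sex, baseline hand function and CST connectivity pattern as closely as possible".

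**The concern.** The prediction for ipsilateral children is a difference of differences: pre-to-post change under CIMT minus pre-to-post change under HABIT. That takes four cell means. A Newman-Keuls comparison takes two. It can compare the arms at one session, two sessions within one arm, or CST patterns averaged over sessions, and none of these is the predicted quantity.

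The ANOVA interaction does address unequal change, but it spreads over all three CST patterns, including bilateral children, for whom no prediction is made. If it is significant, the reader still has to learn whether ipsilateral children account for it and in which direction. The only tool named for that step is Newman-Keuls. At stake is the trial's central directional answer, which could be missed, or assigned to the wrong CST group, through an analytic choice left open in the plan.

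**Working it through.** **Inputs from the documents.** 82 children, 2 arms, 3 CST patterns, 3 sessions, significance level 0.05, smallest detectable difference (SDD) of 5 AHA units (Outcome Measures).

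The target of 82 cannot be reproduced, because no effect size, SD, power or dropout is given. Back-solved for two arms of 41, two-sided 0.05: d = (1.96 + 0.84) x sqrt(2/41) = 0.62 at 80% power, and (1.96 + 1.28) x sqrt(2/41) = 0.72 at 90%. Neither describes a comparison within ipsilateral children, who number about 14 per arm if the patterns are evenly split.

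**Assumptions, not in the documents.** AHA between-child SD 15; correlation between sessions 0.9 (range 0.8 to 0.95), the same for all pairs; equal variances; gain of 6 units; cells of 14/14/13 per arm, since 2 x (14 + 14 + 13) = 82.

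**Step 1: the interaction.** Its df are (2-1) x (3-1) x (3-1) = 4. It is a valid omnibus test. In a separate simulation (SD 10 to 20, SD of change 4 or 6, gain 5 units) it rejected in 4-6% of trials under equal gains. It rejected in 31-69% when only ipsilateral CIMT children gained nothing.

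**Step 2: standard errors for ipsilateral CIMT vs HABIT, 14 per arm.**
- SD of change = 15 x sqrt(2(1 - r)); SE of the contrast on change = SD of change x sqrt(2/14).
- True SE of the post-test difference = 15 x sqrt(2/14).
- SE that the ANOVA's within-subject error would give = sqrt(225 x (1 - r) x 2/14).

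| r | SD of change | SE, contrast on change | True SE, post-test difference | SE using within-subject error |
|---|---|---|---|---|
| 0.80 | 9.49 | 3.59 | 5.67 | 2.54 |
| 0.90 | 6.71 | 2.54 | 5.67 | 1.79 |
| 0.95 | 4.74 | 1.79 | 5.67 | 1.27 |

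At r = 0.9, comparing post-test levels with a between-child error is 5.67/2.54 = 2.2 times less precise than comparing changes. With the within-subject error, the stated SE is 5.67/1.79 = 3.2 times too small for a between-arm difference, so chance baseline differences can look significant.

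**Step 3: power of a planned contrast on change, with no prior gate (t, 82 - 6 = 76 df).** For 8 units: 60%, 88%, 99% at r = 0.8, 0.9, 0.95. For 5 units: 28%, 49%, 79% (simulation gives about 30-77% over the range).

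**Step 4: simulated Newman-Keuls, used only after p < 0.05 on the interaction, arms not matched at baseline.**

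| True state | Method | Ipsilateral CIMT vs HABIT declared different |
|---|---|---|
| Ipsilateral deficit of 8 with CIMT | Newman-Keuls, post-test means, between-child error | about 4-8% |
| Same | Contrast on change | 28-93% |
| Only bilateral children differ, by 10 | Newman-Keuls, 18 means, within-subject error | about 9-52% (false) |
| Same | Contrast on change | about 3-5% (false) |

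If no group's gain differs between arms, the gate holds all of these false flags below about 3%. It does not protect when another CST group opens it, as in the third row.

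**Step 5: baseline balance.** If stratification removes half of the arm difference, the false-flag rate in the third row falls to about 9% (2-23%). If it removes 80% or more, the rate is about 3% or less. Balance does not rescue the first row: with arms fully matched, detection is below 1%.

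**Step 6: pre vs post within each arm.** In the Step 1 simulation, HABIT was significant and CIMT not in 46-96% of trials with the deficit, but also in 2.5-25% under equal gains. The pattern responds to a deficit but does not test a difference between arms.

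**The case against.** A reader might infer that the plan cannot detect unequal response at all. The documents do not support that: the interaction tests it at its nominal level. What is missing is a way to localize and sign the effect.

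A reader might also infer that Newman-Keuls must either miss the deficit or flag it falsely. That is too strong, because each outcome depends on means and an error term that the plan leaves open. With within-subject error and the gate, Newman-Keuls picks up the 8-unit deficit in about 45% of trials at r = 0.9, although part of that comes from the same understated SE.

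Chance baseline differences are not a given either. Allocation is stratified on baseline hand function and CST pattern, which acts directly on them. This stands as a real limit on the false-flag figures. Still, balance on four factors is promised only as far as practicable within each cohort.

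The scenarios are large. With an assumed gain of 6, a deficit of 8 means that ipsilateral children lose 2 units under CIMT. A 10-unit difference in bilateral children is twice the SDD and is predicted nowhere. At 5 units the planned contrast is itself only moderately powered.

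The planned regressions might be offered as the missing test, but no dependent variable or interaction term is given, so they cannot be counted as one.

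**Conclusion.** The point holds as a mismatch between hypothesis and follow-up test. The prediction is a difference in change within ipsilateral children, and no Newman-Keuls pair of score means estimates it. Depending on the unstated means and error term, the follow-up can have low power (about 4-8% against 28-93% for a gated contrast on change) or give false flags (about 9-52%, possibly a few percent if baseline balance is close).

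These figures rest on an assumed SD of 15, correlations of 0.8 to 0.95, about 14 children per cell, and assumed differences of 8 and 10 units. They illustrate the risk and do not predict this trial's results. The change to contrasts is worthwhile, but it will not make the trial well powered for a deficit as small as the SDD.

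**What to change.** Keep the ANOVA. For the hypothesis, replace the Newman-Keuls step with wording such as:

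*The hypothesis will be tested by planned contrasts on change from pre-test to post-test, with change to 6 months secondary: (1) CIMT minus HABIT within ipsilateral children, the key contrast; (2) CIMT minus HABIT within contralateral children; (3) the difference between (1) and (2). Each will be reported with a 95% CI, using the pooled within-cell variance of change as error term. Any contrast in bilateral children is exploratory. Score levels at a single session, or significance within separate arms, will not be used to claim differential response.*

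For the contralateral prediction of equal response, the CI matters more than the p-value, since it shows what size of difference remains compatible with the data. Because AHA and JTTHF are both primary, the plan should also say how the key contrast is handled across the two; the wording above does not settle that.

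The cost is SAP wording only. The contrasts use data already planned for collection and run in the same software. The downside is that all-pairs comparisons of cell means no longer serve the hypothesis.

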Participants will be categorized as having a contralateral CST connectivity pattern if the LI is between 0.9 and 1; i.e., 90% to 100% of the responses in the more affected hand come from the lesioned hemisphere. Participants will be categorized as having an ipsilateral CST connectivity pattern if the LI is between 0 and 0.1; i.e., 0% to 10% of the responses in the affected hand come from the lesioned hemisphere. Participants will be categorized as having a bilateral CST connectivity pattern if the LI is between 0.1 and 0.9.

Transcranial Magnetic Stimulation Analysis

The latency and peak-to-peak amplitude of each TMS pulse will be measured using a suite of custom-written MATLAB (Mathworks, Waltham, MA) scripts. If the latency of the MEP is longer than 40ms after the TMS pulse, that trial will be excluded from analysis. Additionally, if high levels ($>100\mu$ V) of background EMG activity are seen before the MEP, the trial will be excluded from analysis.

Magnetic Resonance Imaging

Each child will receive a structural MR scan (MP-RAGE, 3D, T1-weighted) and diffusion tensor imaging scan, without sedation prior to participation. The structural MRI will be used to co-register TMS stimulation targets with specific brain landmarks, using a frameless stereotaxic neuronavigation system (Brainsight Frameless, Rogue Research, Montreal, QC, Canada). For TMS localization, there is normal variability in brain topography relative to scalp landmarks. MR scans will be done on a Siemens Prisma MRI Scanner (Malvern, PA) in the Citigroup Biomedical Imaging Center (CBIC). Structural scans (165 slices) will be taken at a resolution of 256 x 256 px. The structural MRI will be used to identify the lesion type and extent, as well as to localize the TMS coil (i.e., neuronavigation). The DTI scan will be done during the same session as the structural MRI. For DTI, a 65-direction protocol will be used, 75 slices per direction at a resolution of 112 x 112 px each.

Diffusion Tensor Imaging Analysis

DT images for participants whose CST laterality cannot be determined with TMS due to excessively high threshold or safety reasons will be imported into DTI Studio (Johns Hopkins University) software for processing and analyses. This has been shown to be a reliable surrogate for TMS in determining CST laterality. Image series for each

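### The only named analysis of the continuous laterality index (LI) is a bilateral-only correlation with no treatment term, so it does not test whether LI changes the response to CIMT relative to HABIT

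*Combined protocol and SAP*

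**What the plan says.** Study Objectives sets out an interaction hypothesis. Children with a maintained contralateral CST should respond equally to the two treatments, whereas "children with ipsilateral CST laterality will be less responsive to CIMT than bimanual training".

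The Statistical Analysis Plan assigns this to "A treatment (CIMT, HABIT) x CST connectivity pattern (contralateral, ipsilateral, bilateral) x test session (pre-, post-, 6 month) ANOVA", with repeated measures on session. It adds "Regression analyses will be done to determine predictors of outcomes", naming neither predictors nor interactions. The LI appears once: "For children with a bilateral CST, correlations will be done between the LI and changes in outcome measures". The plan does not say whether the arms are combined or separated, which change is meant (post-test or 6 months), how many bilateral children are expected, or what correlation is of interest.

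The Transcranial Magnetic Stimulation section defines the restriction: "Participants will be categorized as having a bilateral CST connectivity pattern if the LI is between 0.1 and 0.9". Contralateral children have an LI from 0.9 to 1 and ipsilateral children from 0 to 0.1. Children classified by DTI have no LI and can only be contralateral or ipsilateral.

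**The concern.** If laterality changes the response to CIMT relative to HABIT, the slope of improvement on LI should differ between arms. A correlation with no treatment term does not estimate that difference. It also keeps only children with intermediate LI and omits the near-0 and near-1 groups about which the hypothesis makes its predictions.

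What is at stake is interpretation. A null correlation could be taken to support independence from CST organization, which the document's title already asserts, even though such a null would be likely if the hypothesis were true. Conversely, a significant correlation could arise from an LI effect common to both treatments, which is not the hypothesis.

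**Working it through.** **Inputs.** From the documents: N = 82, two arms, significance level 0.05, bilateral band LI 0.1 to 0.9, and an AHA smallest detectable difference of 5 units. Not given, so assumed: 1:1 allocation, two-sided tests, 70 or 82 children with an LI, a bilateral share of 10% to 50%, LI uniform within each band, and a HABIT slope of zero. The CIMT gain is assumed to rise by 0.83, 1.25 or 1.67 residual SD from LI 0 to LI 1 (for example 5 AHA units with SD 6, 5 with SD 4, or 10 with SD 6).

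**Step 1: the plan's own figure.** The plan says "We aim to recruit 82 participants based on sample size calculations", citing "outcomes of a prior CIMT/HABIT randomized controlled trial and pilot data", but gives no effect size, SD or power, so 82 cannot be reproduced. Back-solving for 41 per arm, d = (1.96 + 0.84) × √(2/41) = 0.62 at 80% power, or 0.72 at 90%. This is not a check on the LI analysis, for which no sample size is stated.

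**Step 2: what the correlation responds to.** Simulation with LI uniform on 0.1 to 0.9 and bilateral children only:

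| True within-arm correlation (CIMT / HABIT) | Treatment-by-LI effect? | Mean pooled r | Pooled test rejects, n = 28 |
|---|---|---|---|
| 0.5 / 0.5 | No | 0.50 | 82% |
| 0.5 / 0 | Yes | about 0.26 | 28% |
| 0.5 / −0.5 | Yes, large | 0 | about 4–5% |

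In the last row the rejection rate stays at 4–5% even with n = 82, where a treatment x LI term has about 100% power. Correlating within each arm does not solve this, because two separate p-values do not test a difference in slopes.

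**Step 3: power of a correlation for a given r.** By Fisher z, power ≈ Φ(atanh(r)·√(n−3) − 1.96). With n = 27 (one third of 82):
- r = 0.3: 0.3095 × 4.899 − 1.96 = −0.44, giving 33%.
- r = 0.5: 0.5493 × 4.899 − 1.96 = 0.73, giving 77%.

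For n = 8 to 41 (10% to 50% of 82), power is 11–48% at r = 0.3, 23–92% at r = 0.5 and 49–100% at r = 0.7.

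**Step 4: which r is relevant.** The SD of LI in the bilateral band is 0.8/√12 = 0.231. For r = 0.5 within CIMT, slope × 0.231 must equal 0.5/√0.75 = 0.577, so the slope is 2.5 residual SD across the LI range. At an assumed SD of 6 that is 15 AHA units, three times the smallest detectable difference. With a flat HABIT slope, this gives a pooled r of about 0.26. At n = 23, 0.266 × √20 − 1.96 = −0.77, or about 22% power.

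**Step 5: the assumed scenarios** (6,000 simulated trials each, one third of children in each pattern; power for slopes 0.83 / 1.25 / 1.67):

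| Children with an LI | Pooled bilateral correlation | Treatment x LI, all with an LI |
|---|---|---|
| 70 | 7 / 9 / 12% | 27 / 50 / 75% |
| 82 | 7 / 10 / 14% | 30 / 57 / 82% |

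Type I error was about 5% for both tests. A CIMT-only correlation in the bilateral children has 9 / 13 / 19% (70 with an LI). Across bilateral shares of 10% to 50% and 70 to 82 children, the ranges are about 5–18% against 23–90%.

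**Step 6: comparison with the planned ANOVA.** Same slopes and one-third split, treatment x pattern interaction on change scores (4,000 runs):

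| | Treatment x LI | Treatment x pattern, omnibus | Ipsilateral-versus-contralateral contrast |
|---|---|---|---|
| 70 with an LI, plus 12 DTI-classified in the ANOVA only | 28 / 53 / 77% | 24 / 46 / 72% | 30 / 57 / 81% |
| All 82 with an LI | 31 / 58 / 82% | 20 / 43 / 66% | 27 / 53 / 77% |

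**Step 7: the LI itself.** The Transcranial Magnetic Stimulation section first describes LI as the ratio of lesioned to contralesional responses, then uses it as the proportion coming from the lesioned hemisphere. With 10 responses from each side, the ratio is 10/10 = 1, which would fall in the contralateral band. The proportion is 10/20 = 0.5, which is bilateral.

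**The case against.** The strongest reply is that the hypothesis is tested elsewhere. The ANOVA includes both arms and all three patterns, and Study Objectives makes no prediction for bilateral children. On that view the correlation is a natural supplement: the categories capture nearly all the LI information at the ends, and the correlation looks at gradation in the middle. This stands. A reader might infer that the plan leaves the treatment-by-laterality question untested, and it does not. Step 6 also shows that the large power gap in Step 5 is a gap against the correlation, not against the plan as a whole.

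A reader might also infer that the plan pools the arms. It does not say so; it is silent, and the point does not depend on pooling.

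A third tempting reading is that the correlation has almost no power. The documents cannot show that, since the bilateral count, the SD and the slopes are all absent. A zero HABIT slope is an assumption too, because the objectives constrain the difference between treatments and not the HABIT slope. With a pooled r of 0.5 and 16 to 27 bilateral children, power would be 51–77%.

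Finally, nothing in the plan rests a conclusion of independence on this correlation. That is a risk of later reading and not a stated intention. What survives is that the correlation cannot answer the interaction question, and that the unspecified regression cannot be assumed to do so.

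**Conclusion.** The point holds for the continuous-LI analysis only. As written, the correlation does not test whether the LI slope differs between CIMT and HABIT: a common slope can make it significant, opposite slopes cancel when the arms are combined, and it omits the ends of the range. That conclusion follows from the text and needs no assumption about power.

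The power figures (about 5–18% against 23–90%) are conditional on the assumed slopes, zero HABIT slope, bilateral share and number with an LI. Against the planned ANOVA, the treatment x LI term gains between nothing and a modest amount. This is an inexpensive improvement to a supplementary analysis; it does not show that the primary hypothesis test is missing.

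**What to change.** First reconcile the two descriptions of LI in the Transcranial Magnetic Stimulation section, so that one formula yields the 0-to-1 scale on which the categories depend.

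Then replace the LI sentence with wording such as: *As a supplement to the ANOVA, in all children with a TMS-derived LI, each primary outcome will be regressed on treatment, LI, treatment x LI and the baseline value. The interaction coefficient and the LI slope in each arm will be reported with 95% confidence intervals. The relation between LI and change within bilateral children will be shown descriptively.* Name the test session to which it applies.

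The cost is a few sentences of SAP text and no new data. The downside is small: a linear LI effect is assumed, possibly over clustered values, and DTI-classified children do not enter this model, though they remain in the ANOVA. Power stays limited for small effects, so the intervals should carry the interpretation.
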